21.8	Insurance of the Subjects	56
21.9	Confidentiality	56
22	Appendices	57
23	References.....	90

1 Synopsis of the Clinical Investigation

Introduction

Dental caries is the most widespread of all diseases. It causes destruction of tooth structure by dissolving the enamel on the outside of the tooth first and then progressing into the inside of the tooth. While it is possible to use traditional dental fillings to replace diseased tooth structure, it is far better to slow down or reverse the disease process so that no fillings are needed. One of the most difficult places to use preventive or non-surgical treatment is the contact area between teeth. Recently there is evolving interest in using composites to infiltrate enamel and dentin areas that have just begun to be destroyed by caries. The infiltration technique arrests the lesion progression by sealing the porous surface and restores the damage avoiding ongoing acidic damage of tooth structure.

Objective

Assess the clinical efficacy s of using Icon to infiltrate initial lesions below the tooth surfaces that exist on the contact surfaces between posterior teeth as a means of stabilizing diseased tooth structure and arresting further lesion development.

Materials and Methods

One hundred fifty volunteers (14+ years) with two early lesions in posterior teeth will be enrolled into a clinical trial to evaluate the clinical efficacy of infiltrating the lesions as compared to current watch-and-wait approaches that are combined with good oral hygiene and fluoride application. Each subject will have a treated lesion and a control lesion. Only small early lesions without clinical signs of surface cavitation will be selected. The control lesions will be stabilized through a normal preventive regimen, while the treatment lesions will be infiltrated with a resin. Lesion status will be monitored every six months by clinical examination and as well using annual radiographs.

Clinical Significance

Infiltrating a caries lesion is a potential effective strategy to strengthen damaged tooth structure and to reduce caries progression without any surgical intervention.

1.1 Description of the CIP

The objectives of the CIP are to provide a full description of the planned clinical trial. The preceding short narrative (Synopsis) introduced the goal of the project and its approach to investigate the clinical efficacy of management of early caries lesions by resin infiltration.

1.4 Abstract

This is a three year single site clinical evaluation of a FDA approved (510(k):K100062) lesion penetrating resin used to infiltrate and hamper progression of proximal carious lesions. The purpose of this study is to compare lesion progression infiltrated with (Icon, Hamburg, Germany) to a similar sized lesion in the same patient treated with a placebo. The study is designed as a randomized, controlled, prospective clinical trial with a three year follow-up evaluation period.

The clinical site will enroll 150 subjects (in the age range of 14 years or older) with 2 study lesions. The patients will be evaluated at six time points over a period of 3 years. Lesion status and caries risk will be monitored at 6-month intervals, while radiographic evaluation will be conducted at 12-month intervals at 1-, 2- and 3-year recall visits.

This controlled trial will assess the positive effects of caries lesion infiltration by Icon and may open a new therapeutic strategy in dentistry to establish a micro-invasive therapy.

CIP <NCT01988337>

Author: [REDACTED]

[REDACTED]

2.2 Chemical Composition

2.2.1 Chemical Composition Infiltrant (Resin)

[REDACTED]

[REDACTED]

[REDACTED]	[REDACTED]
[REDACTED]	[REDACTED]
[REDACTED]	[REDACTED]

[REDACTED]

[REDACTED]

2.2.2 Chemical Composition Ethanol Solution (Dry-it)

[REDACTED]	[REDACTED]
[REDACTED]	[REDACTED]

[REDACTED]

[REDACTED]

2.2.3 Chemical Composition HCl Etching Gel (Hydrochloric Acid Gel)

[REDACTED]

[REDACTED]

[REDACTED]	[REDACTED]

[figure not shown]
[REDACTED]

[REDACTED]

[REDACTED]

[REDACTED]

2.3 Instructions for use

3 Objectives of the Clinical Investigation Plan (CIP)

The objectives of the CIP are to provide a full description of the planned clinical trial. The preceding short narrative (Synopsis) introduced the goal of the project and its approach to investigate the clinical effectiveness of management of early caries lesions by resin infiltration. The Background and Rationale section addresses the relevance of the project to oral health and the rationale for the proposed project. The existing knowledge is briefly stated, including literature citations and highlights of relevant data, indicating the gap that the project is intended to fill. The research plan includes the Study Design and Methods addressing the hypotheses to be tested, followed by Specific Aims. The data collection and analysis (including assessment of statistical significance) will be described and used to prove or disprove the hypotheses. Previous experience with the materials involved is described including attention to risk analysis. Expected results, potential difficulties and limitations are discussed and solutions or alternative approaches indicated.

Project Overview and Professional Support

Based on internationally accepted protocols we have designed a prospective, randomized controlled clinical trial (RCT) to investigate the effect of a novel infiltration method as an alternative treatment option for early caries lesions. The Clinical Investigation Protocol for this study includes all components and documentation as required to conform to international standards for clinical research (CONSORT], ISO/DIN 14155:2011 and Good Clinical Practice Guidelines.²⁰⁻²²

4 Preliminary Investigations and Justification of the CIP

4.1 Background and Rationale

Fissure sealing has been shown to inhibit not only the formation of occlusal caries but also to impede the progression of existing caries lesions.²⁷⁻²⁹ Pit-and-fissure sealants are an effective way at preventing caries in children and adults—even in early noncavitated (incipient) lesions, according to a new set of ADA evidence-based clinical recommendations.³⁰ Lately, the concept of sealing caries to arrest lesion progression has been transferred to approximal surfaces.^{31,32} In a clinical study sealed approximal lesions showed significantly reduced progression after 18 month compared with those that were treated only with preventive measures.³² In addition, it has been shown in contemporary European populations that lesions, radiographically progressed into dentin, were not cavitated in 60% of the cases.³³ This indicates that non-invasive management of such lesions is preferred above invasive operative-restorative treatment options. The pores of enamel caries lesions provide diffusion pathways for acids and dissolved minerals. The aim of lesion infiltration is to occlude these pores by infiltration with light curing resins in order to block the diffusion of acids into the lesion body.³³⁻³⁴ In contrast to sealing of caries, caries lesion infiltration aims to occlude the pores within the lesion rather than placing a diffusion barrier on the lesion surface. Several in-vitro studies showed significantly reduced progression of infiltrated enamel lesions in demineralizing environments.³⁵⁻³⁶ Caries results from a dynamic series of demineralization and remineralization cycles when demineralization dominates. Demineralization initially produces a small non-cavitated area on enamel (white spot lesion) which can progress to a cavitated lesion unless remineralization dominates. In the initial lesion development white spot lesions have an intact hypermineralized surface with subsurface demineralization. As demineralization continues, surface enamel cavitates and this defect must be restored to create proper form and function to the tooth. Caries is a multifactorial disease caused by cariogenic bacteria established in the oral biofilm. These bacteria²³ metabolize sucrose or other cariogenic carbohydrates (fructose or glucose) and secrete organic acids (lactic, propionic, and formic) that cause mineral ion loss (calcium and phosphates) and demineralization of the tooth. Mineral lost by this method can be replaced during periods of neutral pH (remineralization) from calcium and phosphates in the saliva. Remineralization is facilitated by fluoride and can arrest carious demineralization in enamel by the formation of a hard outer surface. Periods of demineralization and remineralization make up a continuous cycle by which minerals in tooth structure are removed and replaced. If the balance is tipped toward demineralization, carious lesions develop.

The caries process in dentin is similar to enamel, except that dentin demineralization begins at a higher pH (6.4, compared to 5.5 for enamel) and proceeds about twice as rapidly; this is because dentin has only half the mineral content of enamel. Low fluoride levels²⁴ are insufficient to initiate dentin remineralization but are adequate to facilitate enamel remineralization. Fluoride-ion concentration in saliva is low, averaging about 0.03 ppm (1.6 pmol/L) in the normal subject. In enamel, at fluoride levels around 3 ppm²⁵⁻²⁶, if adequate calcium is present the balance of mineral uptake and loss is shifted from net demineralization to net remineralization.

Dental decay is a slowly progressing disease taking several years to advance through the enamel into the dentin of permanent teeth. Progression of caries through enamel and dentin are variable and depend upon the amount of saliva, oral hygiene practices, fluoride use as well as the frequency of sucrose intake, however if proximal caries has reached the inner part of the enamel radiographically, it is difficult to halt further progression and many lesions having reached this stage are restored.

This is based partly on the assumption that carious lesions once reaching dentin will continue to progress and that a restoration is necessary at this stage. A Swedish longitudinal study following teenagers that participated in a rigorous oral hygiene program were clinically and radiographically followed during a 15-year period.²⁷ Even with this high level of preventive care, many had progressing proximal lesions. For a long time sealants have been used to prevent caries on occlusal surfaces with great success. Sealants have also been successfully used therapeutically when initial or even moderately deep occlusal caries developed.^{28,29} Sealing lesions on smooth surfaces has also been tried *in vitro* and the suggestion was that such an approach might delay lesion progression rather than arrest the lesion.³⁰⁻³² The latter authors suggested adopting the sealing approach of initial carious lesions on proximal surfaces. There are many possibilities for stopping or reversing the advancement of the lesion. For non-cavitated lesions, remineralization is the natural repair process that relies on the local environment: sufficient saliva flow, availability of calcium and phosphate ions, fluoride, microflora and optimal environmental pH to rebuild a new surface after demineralization. However, if the environment favors demineralization the lesion will continue and cavitate spreading to dentin. Due to the structural difference of dentin, lesions in dentin progress more rapidly than enamel lesions requiring earlier intervention. Improvements in dental materials are promising but there is yet to be a material that carries all mechanical and physical characteristics of the natural tooth. Therefore, it is important to maintain the structure and arrest lesions before they advance. Lesion treatments of enamel caries focus on remineralization using topical applications of fluoride or amorphous calcium phosphate and emphasizing oral hygiene procedures. However, the success of these treatments is dependent on the patient's compliance which is especially difficult in the

proximal areas, where plaque removal is more difficult. Typically, most clinicians will observe small proximal lesions which are located entirely in enamel and typically recommend preventive measures rather than restoration. If the subject is lost to recall and the lesion continues, a larger lesion develops which requires restoration. Treating carious tooth pulp exposures is consequential, often requiring either extraction or root canal therapy. Both the loss of the tooth and its replacement, or endodontic treatment and tooth restoration, involve multiple appointments and considerable expense. A procedure which does not depend upon patient's compliance would be a micro-invasive treatment such as resin infiltration of the subsurface lesion which would eliminate dependence on the patient's compliance. A newly developed surface infiltrating resin has been developed by DMG (Hamburg, Germany). The infiltration technique has significant advantages since it is a non-invasive system requiring no irreversible removal of tooth structure and eliminates drilling and most pain associated with tooth restoration. Evidence is building that this system stops or slows the proximal carious lesion progression. Paris and Meyer-Lückel evaluated the effectiveness of resin infiltrated carious proximal lesions in an 18 month study using standardized radiographs and digital subtraction.¹² They concluded that a resin infiltration into the inner half of enamel or the outer third of dentin is an effective way to reduce carious lesion progression.³³ Martignon et al, using a radiographic comparison technique, reported that a caries infiltrating resin was more effective method for treating proximal enamel lesions than sealing or flossing over a two year period.^{8,34} Ekstrand et al compared resin infiltration and fluoride varnish to fluoride varnish only in primary molars after one year. Resin infiltration and fluoride varnish was 35% more effective than fluoride varnish alone.^{8,35} Alkilzy and Spliedt reported that caries infiltration provided a simple, minimally invasive method for treating proximal initial caries.³⁶ The objective of this three year study is to evaluate the efficacy of sealing initial proximal lesions.

Clinical Significance

Infiltrating a caries lesion is a potentially effective strategy to strengthen damaged tooth structure and to reduce caries progression without any surgical intervention. Management of early lesions by infiltration instead of or postponing restorative treatment would have a great impact towards improving oral health care by means of its non-invasive nature. It will drastically lengthen the life-cycle of a tooth. Infiltration would provide a simple and cost-effective management option with the least possible iatrogenic effect and diminished need for future re-treatment due to deteriorating of restoration margins. There are only few clinical data reported comparing the recent development to

infiltrate lesions with a standard preventive regimen. Therefore, a randomized controlled clinical trial is warranted to study lesion progression with and without resin infiltration, while the patients receive standard-oral care hygiene treatment, diet counselling and fluoride regimen.

4.2 Hypotheses

The objectives of the investigation are to study the short-term clinical performance of resin infiltrated teeth in a caries-active environment. We hypothesize that in a high caries risk population and with a regular preventive regimen as control management the infiltration of early approximal caries lesions leads to arrest of the lesion and reduction of lesion progression.

4.2.1 Hypothesis I

Infiltrated early caries lesions in a high caries risk population have a lower incidence of lesion progression when compared to lesions managed by regular preventive regimen. The number of lesions requiring an invasive intervention (filling) is significantly lower than for lesions treated with standard regimens.

4.2.2 Hypothesis II

Infiltrated early caries lesions in a high caries risk population have a lower rate of lesion progression when compared to lesions managed by regular preventive regimens.

4.3 Previous Experience with the Study Material

4.3.1 Description of the clinical procedure

The proposed components of the infiltration kit are substantially equivalent to a variety of currently marketed dental materials in terms of physical and mechanical properties. The *indication for use* of the DMG "Infiltration kit for caries lesions" is micro-invasive treatment of early approximal caries.

The FDA approved (510(k): K100062) materials will be used according to the label.

4.3.2 Preclinical Testing

The materials to be used for infiltration (etchant and infiltrant) have received EEC market authorization for medical devices [REDACTED]. Therefore, complete documentation of preclinical testing and biological evaluation of the device and its results has passed the appropriate regulatory bodies. Documentation and approvals are on file with the sponsor (510(k): K100062).

4.3.3 Previous Clinical Experience

The devices used in this study have seen clinical application for several years for infiltration indication with excellent results. The materials in the infiltration kit will be used according to label and for approved indication (micro-invasive treatment of early proximal caries).

4.3.4 Clinical Studies

Infiltrating a caries lesion is a strategy to strengthen damaged tooth structure and to reduce caries progression without any surgical intervention.¹⁻³ Management of early lesions by infiltrating instead of or postponing restorative treatment would have a great impact towards improving oral health care by means of its non-invasive nature. It will drastically lengthen the life-cycle of a tooth.³ Infiltration would provide a simple and cost-effective management option with the least possible iatrogenic effect and diminished need for future re-treatment due to deteriorating of restoration margins.⁴

The promising *in vitro* results of caries infiltration on extracted teeth were underlined by different clinical trials. Several groups reported slower caries progression in infiltrated sites compared to controls: Radiographically obtained quantification reveals lesion progression in 16% of infiltrated sites compared to 53% for controls after one year and for 24% (infiltration group) and 62% (control) after two years. Recently, the three year follow-up data were published, reporting 32% progression for infiltrated lesion and 70% for controls in this split-mouth study.⁵ Meyer-Lueckel et al. measured progression rates of 7% (infiltrated sites) and 37% (controls) after 18 month in young adults.⁶ The currently available 3-year data of this study report 4% progression in infiltrated lesion and 42% for controls.⁷ Ekstrand et al. aimed to assess the efficacy of resin-infiltrated lesions covered by fluoride varnish (FV) versus FV treatment only of proximal lesions on deciduous molar teeth in a one year

split-mouth study. Radiographically, 23% of the test lesions and 62% of the control lesions had progressed, comparable to the aforementioned results in young adults.⁸

5 Device Risk Analysis and Assessment

5.1 Risk Analysis of the Medical Device

There is a minimal risk associated with the device itself and the procedures involved in its use, as identified by risk assessment and post-market experience of substantially equivalent materials, beyond the common risks related to standard dental treatment.

Definition: Minimal risk is the probability and magnitude of harm or discomfort anticipated in the research and not greater in and of themselves than those ordinarily encountered in daily life or during the performance of routine physical or psychological examinations or tests [45 CFR 46.102(i)]

The entire treatment in each aspect, including lesion size and location, all materials, equipment and techniques used, is part of regular daily life. Dentist visits, like in this study, resulting in caries detection, diagnosis and management by regular preventive regimen or sealant are not at all out of the ordinary. It is –alas- rather ubiquitous and a common part of daily oral health care provisions that our professions provides to the public. Therefore, the risk is NOT greater than routine dental practice. The care provided meets this definition of minimal risk.

5.2 Risk Management of the Clinical Device

Although the exclusion criteria mention allergy to methylmethacrylate (a commonly used monomer as a component in many commercial medical, dental, and non-medical applications), this allergy has a low prevalence and materials containing methylmethacrylate or its analogues are managed routinely in dental practices around the world every day. In the case of the rare occurrence of an allergy, patients are isolated immediately from contact, treated using well-known emergency procedures, and recover quickly. In almost every case, a patient knows in advance that they have these types of allergies because they must avoid contacts with a huge number of acrylic materials present normally in world as parts of garments, containers, and common household items. No other adverse effects are known, and none are anticipated.

6 Objectives of the Clinical Investigation

6.1 Objectives

The main purpose of the present study is to evaluate the efficacy of the Icon Caries Infiltration system, DMG, Hamburg, Germany) in controlling the progression of non-cavitated proximal lesions in posterior teeth.

6.2 Specific Aimes (Primary Endpoints)

6.2.1 Specific Aim I

Significant lower rate of invasive interventions (filling) compared to standard treatment

6.2.2 Specific Aim II

Change in lesion size (Radiographic analyses)

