11.4 Statistical Analysis

11.4.1 Descriptive Statistics

For the digital subtraction procedure, the ANOVA for Repeated Measures, will be used to determine significance between the two groups ($p=.05$). The remaining endpoints will be listed as percentages rather than subjected to statistical analyses.

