11.4.3 Evaluation of Records

This section was revised and specified in Amendment 1 valid as of 30.11.2015!

The outcome variable will be the caries progression status (regression, no changes or progression) for the selected lesions after 3 years. The radiographs will be read by 2 methods (1) visual independent reading and (2) subtraction radiography of digitized images.

For visual readings the depth of each selected lesion will be visually assessed and recorded by the PI independently on the conventional baseline and follow-up radiographs, respectively. The depth of the selected lesion will be classified into the following scales 1- lesion regressed, 2- lesion expanded, 3 no change in lesion size. A score of 4 (missing surface, generally fractured) and 5 (presence of a restoration) may be assigned when needed. For all visual readings, the examiner will be blinded as to whether the examined radiograph was a radiograph of the lesion was Icon sealed or a control. The examiner will be asked to determine the status (1 to 5) of the right positioned image against the left positioned image of the radiograph.

To assess the progression status on subtraction images the conventional radiographs will be first digitized (Epson Expression 1680 Pro scanner, Photoshop software) in a standard way (TPU format, 8-bit, 3,200 resolution), and contrast and gamma levels will be pre-adjusted pair-wise in the baseline and follow-up images. The images will be stored uncompressed (TIFF 3,650 x 2,425 grayscale) at an individual size of 9–14 Mb. Next, the images will be converted to a readable format for the subtraction software in Adobe Photoshop 6.0 and stored as TIFF 600 x 400 files, with a code corresponding to case number, test/control lesion, baseline or follow-up and involved surface.

The digital subtraction of the digitized images will be undertaken by one of the examiners by means of the Compare software (Dental Health Unit, University of Manchester, UK), which runs as a plug-in to the Image Tool software, version 1.23 [University of Texas Health Science Center at San Antonio,

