A previous infiltration study by Martignon et al. [5] reported a 3-year difference of proportions of 37.8% (95%CI: 20.5-55.2%) with (resin infiltration (68%) vs. control (30%)). Based on this and with alfa = 0.05 and a power of 80% the calculated sample size (t-test; matched pairs) would be 23 lesion pairs (thus 23 participants) to find significant differences. However, this study aimed to enroll 150 participants to not only allow for a potentially high attrition rate (20%) over a period of 3 years, but also aiming to better quantify the efficiency of the treatment effect.

Statistical Analysis

All evaluations are performed by two trained and calibrated examiners. The primary outcome is proportion of lesions that required restorative treatment (filling) after 3 years as measured via dental examination. Differences between groups will be tested using Fisher's exact test and ANOVA for Repeated Measures for subgroup analysis based on caries risk. Secondary outcomes are change in categorical lesion depth (progression to next depth category lesion; E1->E2->D1->D2->filling) after 6 months and 1, 2 and 3 years as measured by pairwise comparison of radiographs as well as the influence of Icon treatment on clinical parameters. Differences will be analyzed with McNemar's test with 95% confidence interval (95% CI) and P = .05.

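### The protocol and the SAP disagree on which endpoint decides the trial, fillings or radiographic change, and no rule links the two

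*Combined protocol and SAP*

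**What the plan says.** Protocol 6.2, under a heading that names primary endpoints, gives Aim I as "Significant lower rate of invasive interventions (filling) compared to standard treatment" and Aim II as "Change in lesion size (Radiographic analyses". Secondary endpoints have their own list in 6.3, so Aim II is not simply a misfiled secondary. Section 6.1 gives the main purpose as control of lesion progression.

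Protocol 11.4.1 says: "For the digital subtraction procedure, the ANOVA for Repeated Measures, will be used to determine significance between the two groups", at 0.05. It continues: "The remaining endpoints will be listed as percentages rather than subjected to statistical analyses". On that text fillings receive no test.

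Protocol 11.4.3 says: "The outcome variable will be the caries progression status (regression, no changes or progression) for the selected lesions after 3 years".

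The SAP, under Statistical Analysis, says: "The primary outcome is proportion of lesions that required restorative treatment (filling) after 3 years as measured via dental examination". It adds: "Differences between groups will be tested using Fisher's exact test". Radiographic depth moves down a level: "Secondary outcomes are change in categorical lesion depth". Those changes are tested with McNemar's test at 0.05.

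The SAP's sample size rests on 68% against 30% at three years. These are the complements of the 32% and 70% radiographic progression quoted in protocol 4.3.4, so the trial was sized on the outcome that the SAP calls secondary.

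**The concern.** Fewer fillings and less radiographic progression are different claims. A plan must say which of them decides the trial, or how the two combine. Here each document supports a different answer, and the visible text contains no rule to settle it. Whoever reports the trial could choose the deciding endpoint after seeing the data and cite a governing text for either choice.

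Two things are at stake. The first is the verdict: a trial significant on one endpoint only is a success under one document and a failure under the other. The second is the error rate: if either endpoint is allowed to count, the chance of a false claim is no longer held at 5%.

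The point concerns the decision rule across the endpoints. Whether Fisher's test suits paired lesions is a separate matter.

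**Working it through.** **1. The texts side by side**

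| Source | Fillings | Radiographic change |
|---|---|---|
| Protocol 6.2 | primary | primary |
| Protocol 11.4.1 | percentage, no test | digital subtraction, tested at 0.05 |
| Protocol 11.4.3 | score 5 on the reading scale (restoration present) | the outcome variable |
| SAP, Statistical Analysis | sole primary, Fisher | secondary, McNemar at 0.05 |
| SAP, Sample Size Determination | no rate given | basis of the calculation |

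Neither document on its own tests two primary endpoints. The conflict appears when they are read together.

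**2. The plan's own figure**

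Inputs from the SAP: 68% against 30%, difference 0.378, alpha 0.05, power 80%. Sidedness is not stated; two-sided is assumed.

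- SD of the paired difference without within-pair correlation: √(0.68×0.32 + 0.30×0.70) = √0.4276 = 0.654.
- n = ((1.960 + 0.842) × 0.654 / 0.378)² = 23.5. With a difference of 0.38 it is 23.2.

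Rounded up this is 24, against the stated 23 pairs, so the figure reproduces closely. It confirms that the calculation concerns progression and not fillings. Expected completers are 150 × 0.8 = 120 pairs.

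**3. False-positive risk if either endpoint may count**

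For two independent tests at two-sided 0.05: 1 − 0.95² = 9.75%. Positive correlation lowers this (bivariate normal):

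| Correlation | 0 | 0.3 | 0.5 | 0.8 | 0.9 | 1 |
|---|---|---|---|---|---|---|
| Either test significant | 9.75% | 9.51% | 9.07% | 7.81% | 7.04% | 5% |

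The correlation is not given but should be positive. Table 14.2 links a filling to deep progression, and the SAP's depth scale ends in a filling. Counting only false findings in favour of Icon, the risk is 4.9% at correlation 0 and 4.5% at 0.5, against 2.5% for a single two-sided test.

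The tests also matter. These null simulations used 120 pairs, with fillings as a subset of progressed lesions. All rates are assumed: progression 30–50%, fillings from 10% up to 25%, within-pair latent correlation 0 or 0.3.

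| Fillings / progression tests | Either-test rate |
|---|---|
| Fisher / exact McNemar | about 6% (runs from 5.1% to 6.7%) |
| Fisher / asymptotic McNemar | about 7% |
| Asymptotic McNemar on both | about 9–10% |

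**4. How often the two verdicts differ**

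Inputs: 120 pairs and progression of 32% against 70% (protocol 4.3.4). The share of progressed lesions that are filled is assumed to be the same in both arms, because the documents give no filling rate. Power on progression is essentially 100%, so the split rate is 1 minus the power on fillings (Fisher):

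| Share of progressed lesions filled | Power, fillings | Positive on progression only |
|---|---|---|
| 10% | 17% | 83% |
| 20% | 41% | 59% |
| 30% | 64% | 36% |
| 40% | 81% | 19% |
| 50% | 92% | 8% |

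Separate simulation runs move each end by a point or two, giving about 85% down to 9%.

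**5. Error under a stated rule**

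- One primary, a fixed order, or both required: at most 5%.
- 0.025 each: 1 − 0.975² = 4.94% if independent, and never above 5%.

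**The case against.** The strongest reply is that no multiplicity problem exists in either document. The SAP has one primary endpoint and a nominal 5% error. Under protocol 11.4.1 only the subtraction analysis is tested. This is correct, and it limits the point: a reader might infer that the trial runs a false-positive risk of about 9%, but the documents do not support that as a plain statement. It requires merging the two documents, letting either endpoint count, and using tests less conservative than the SAP's Fisher test.

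A reader might also infer that a split verdict is the likely result. That follows only if a small share of progressed lesions is filled. No filling rate is given, and at a 50% share the split is rare.

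Section 11.4.3 is weaker evidence than 6.2. It describes how radiographs are read, so its outcome variable may mean only the radiographic variable. It is also marked as revised by Amendment 1, and the text of Amendments 1 and 2 cannot be seen here. The statement that no rule exists therefore covers visible text only. Section 6.2 carries no such mark, however, and its conflict with the SAP stands in current text.

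Finally, making fillings the sole primary demotes the endpoint on which the trial was sized. That is a real cost, and the choice belongs to the sponsor.

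**Conclusion.** The point holds as an unresolved contradiction over which endpoint decides the trial. Protocol 6.2 names two primaries, 11.4.1 tests only the radiographic one, and the SAP makes fillings the sole primary while sizing the trial on progression. Nothing visible ranks the documents or the endpoints, so the deciding endpoint remains open after the data are seen.

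The size is conditional. The 9.75% ceiling applies only if both endpoints are tested at two-sided 0.05 and either may count; about 6–7% is more realistic with Fisher's test for fillings. The split-verdict range of about 85% to 9% rests on an assumed 10–50% of progressed lesions being filled, on the cited 32% and 70%, and on 120 completing pairs. The contradiction itself needs none of these assumptions. It should be corrected, and wording is enough.

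**What to change.** Before analysis, make 6.2, 11.4.1, 11.4.3 and the SAP state the same hierarchy.

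- **Default, following the SAP:** the proportion of lesions filled by 3 years is the sole primary endpoint, at two-sided 0.05. Change the 11.4.1 sentence on percentages so that fillings are formally tested; otherwise the conflict remains. Relabel Aim II as the key secondary endpoint, 3-year radiographic progression. Test it at two-sided 0.05 only if the primary is significant; if not, report the estimate with a 95% CI and make no confirmatory claim. Name the radiographic reading meant, since 11.4.1 tests subtraction and the SAP tests depth category.
- **If both are to stay primary:** state an alpha split, for example 0.025 each, or require both to succeed.

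The change is to wording only. Under the default, a radiographic result alone can no longer be called trial success. A filling test of uncertain power (17% to 92% over the assumed range) may also block a confirmatory claim on the endpoint used for sizing. An alpha split should cost little on progression, where 120 pairs are expected and about 23 were calculated as enough. Its cost on fillings cannot be judged without a filling rate, so the sponsor should state the rate it expects when it chooses.
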